## 6.4 Pharmacokinetic Evaluations

No pharmacokinetic data were collected in this study.

## 6.5 Safety

Safety analyses will be tabulated by as-treated treatment group and overall, unless specified otherwise. Results for treated subjects on DBT will be tabulated by as-treated treatment group without overall treatment group.

Safety outcome measures will include deaths, AEs, laboratory tests, vital signs, physical measurements, electrocardiograms (ECGs), and S-STs.

Safety analysis periods are pre-treatment, pre-rimegepant treatment, on-DBT, on-OL rimegepant, on-treatment (on-DBT and on-OL rimegepant combined), on-rimegepant (DB or OL), post-DBT pre-OL rimegepant, and follow-up (see Section 7.4).

- For the blinded interim analysis in the 90-Day Safety Update, safety analysis periods of primary interest will be on-DBT, on-OL rimegepant, on-treatment, and follow-up.
- For unblinded analyses in CSRs, safety analysis periods of primary interest will be on-DBT, on-rimegepant, and follow-up.

Measurements will be slotted into analysis periods based on “measurement date”, which is (1) imputed start date for AEs, (2) death date for deaths (see Section 7.3), and (3) collection or assessment date for all other safety parameters.

Select safety parameters will be summarized as continuous parameters at baseline and each scheduled visit over time in the various safety analysis periods. Measurements will be slotted into safety analysis periods and analysis windows as follows:

- For treated subjects, measurements will be first slotted into the on-DBT, on-OL rimegepant, and follow-up safety analysis periods. Next, measurements will be slotted into analysis visit windows in these analysis periods.
- For rimegepant treated subjects, measurements will be first slotted into the on-rimegepant and follow-up safety analysis periods (see Section 7.4). Next, measurements will be slotted into analysis visit windows in these analysis periods.

If a subject has multiple values in an analysis visit window in a safety analysis period, then the non-missing value in the analysis period closest to the target date for the visit will be used; in the case of a tie, the latest value collected (from the central laboratory, if applicable) will be used. Results will also be shown at EOT for each phase, i.e., last non-missing measurement in the on-DBT, on-OL rimegepant, and on-DB or OL rimegepant safety analysis periods. Results will also be shown at end of follow-up (EOFU), i.e., last non-missing measurement in the follow-up safety analysis period.

In analyses of the worst abnormality or category in a safety analysis period, subjects must have a non-missing measurement in the safety analysis period to be included for a given parameter. In

---

shift from baseline analyses, subjects must have a non-missing measurement at baseline and in the safety analysis period to be included for a given parameter.

See Sections 6.2.5, 7.4, and 7.5 for the definitions of baseline, safety analysis periods, and analysis visit windows, respectively.

By-subject listings of safety data will include safety analysis period (i.e., pre-treatment, on-DBT, on-OL rimegepant, and follow-up), study day, rimegepant study day, COVID-19 visit impact code for visits impacted by COVID-19 (see Section 9.1.5.2), and are described in subsections. In addition, a by-subject listing of procedures will be provided for enrolled subjects.

A by-subject listing of safety narrative subject identifiers will be provided for enrolled subjects with select events, as described in the BHV3000 Core SAP. The listing will flag subjects with select events.

### **6.5.1 Adverse Events**

Refer to the BHV3000 Core SAP for AE start date imputation, AE counting rules, definition of treatment-emergent adverse events (TEAEs), definition of exposure-adjusted multiple occurrences of unique AEs, definition of AEs related to study drug, and AE listing contents.

AEs will be displayed in tables and listings by SOC and PT, unless specified otherwise. AEs by SOC and PT on DBT will be displayed in descending order of rimegepant frequency within SOC and PT, unless specified otherwise. AEs by SOC and PT on OL rimegepant, on rimegepant, on treatment, and during follow-up will be displayed in descending order of overall frequency within SOC and PT, unless specified otherwise. TEAEs on DBT are those that developed, worsened, or became serious on DBT relative to pre-treatment. TEAEs on DB or OL rimegepant are those that developed, worsened, or became serious on DB or OL rimegepant relative to pre-rimegepant. TEAEs on OL rimegepant are those that developed, worsened, or became serious on OL rimegepant relative to pre-OL rimegepant.

A by-subject listing of all AEs will be provided for enrolled subjects that will flag on-DBT TEAEs and on-OL rimegepant TEAEs. Additional by-subject AE listings will be provided for SAEs, AEs leading to study drug discontinuation for treated subjects, hepatic-related AEs, and AEs of special interest (i.e., potential drug abuse AEs, CV, suicidality).

#### **6.5.1.1 Deaths**

Deaths will be identified from any of the following sources:

- AE CRF: PT or reported term containing “death”, outcome of fatal, “yes” response to the question “Did the AE result in death?”, or non-missing death date.
  - DB Subject Status CRF: death as primary reason for phase completion/discontinuation; or death as reason for completing the DB phase through Week 12 and not entering the OL phase.
  - OL Subject Status CRF: death as primary reason for phase completion/discontinuation.
-

- Follow-up Subject Status CRF: death as primary reason for phase completion/discontinuation.

Deaths will be tabulated by safety analysis period for enrolled subjects as follows: by treatment group for treated subjects; not treated; and overall. Counts will be displayed without percentages.

A by-subject listing of deaths will be provided for enrolled subjects, and will display all CRF sources of death, safety analysis period, death date (see Section 7.3), study day derived from the death date, rimegepant study day derived from the death date, and the following AE parameters: non-imputed start date; end date; SOC; PT; verbatim term; outcome; and response to the question “Did the AE result in death?”.

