    - Efficacy date: (1) Complete reference time point date from any question from the evening report headache log or follow-up headache log, or (2) non-missing OL rimegepant date on a non-scheduled day (see Sections [7.6.2.2](#) and [7.6.2.3](#)).
    - OP start date: Earliest reference time point date from the OP epoch.
    - OP end date: Latest reference time point date from the OP epoch.
  - Miscellaneous composite dates
-

- Last DBT visit date: Maximum of the following: (1) latest eDiary reference time point date < OL rimegepant start date; (2) latest complete visit date from Visit Date CRF records without “follow-up” in foldername and visit date < OL rimegepant start date. This will be used to assess eDiary compliance.
- Last OLE visit date: Maximum of the following: (1) latest eDiary reference time point date ≥ OL rimegepant start date; (2) latest complete visit date from Visit Date CRF records without “follow-up” in foldername and visit date ≥ OL rimegepant start date. This will be used to assess eDiary compliance.
- Last DB or OL rimegepant visit date: Maximum of last DBT visit date and last OLE visit date for subjects whose as-treated treatment group is rimegepant; last OLE visit date/time for subjects whose as-treated treatment group is placebo. This will be used to assess eDiary compliance.
- Last contact date: (1) Earliest complete death date from the AE CRF, if it exists; (2) otherwise, the maximum complete date of the following: AE start/stop; COVID-19 visit only for in-person or remote visits; ECG; eDiary reference time point; informed consent; IWRS randomization; laboratory collection; menstrual period start/stop; non-study medication start/stop; physical measurement; procedure; rating scale; questionnaire; study completion/discontinuation from Subject Status CRF (DBT, OLE, follow-up); vital sign; visit.
- COVID-19 visit date: (1) Complete record date, if it exists; otherwise, complete date the visit was planned to occur for a missed visit (see Section 9.1.1).
- Death date: Last contact date derived only for subjects who died (see Section 6.5.1.1).

No imputations are performed on these derived dates. Complete dates are those with valid, non-missing day, month, and year.

See Section 7.6.2.1 for the reference time point date/time and epoch derivations.

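### SAP 6.5.1.1 lets the word 'death' in an adverse event term classify a subject as dead with no other evidence, so a living subject could enter the deaths table

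*SAP*

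**What the plan says.** SAP 6.5.1.1 opens with "Deaths will be identified from any of the following sources". The sources are the AE form and the double-blind, open-label and follow-up Subject Status forms. The AE form entry begins "AE CRF: PT or reported term containing “death”, outcome of fatal" and ends with a yes "response to the question “Did the AE result in death?”, or non-missing death date".

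The result feeds a table: "Deaths will be tabulated by safety analysis period for enrolled subjects as follows: by treatment group for treated subjects; not treated; and overall". The table shows counts without percentages. A by-subject listing "will display all CRF sources of death, safety analysis period, death date (see Section 7.3"), together with AE details that include the verbatim term, the outcome and the answer on whether the event resulted in death.

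Two other sections depend on this rule. SAP 7.3 has "Death date: Last contact date derived only for subjects who died (see Section 6.5.1.1"). SAP 6.5, which sets the date used to place each measurement in a safety period, gives "2) death date for deaths (see Section 7.3").

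**The concern.** A word search on free text does not establish that the subject died. Investigators write verbatim terms in their own words, and the word can appear because someone else died or because the subject was thinking about death. The trial has a plausible route to the second kind. Protocol 6.2.5 has the suicidality scale completed repeatedly and requires an event to be recorded as an AE or SAE when the investigator judges the subject to be at risk. A verbatim such as *thoughts of death* would be a natural way to write that down. Both kinds of wording are hypothetical examples.

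At stake is the accuracy of the deaths table, where a single entry is conspicuous. The AE overview in SAP 6.5.1.2 has no row for fatal events, so it gives no parallel count against which the table could be checked.

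**Working it through.** The plan gives no figure on this point to reproduce. The check is to read the rule literally, apply it to test records, and follow the date and period derivations.

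**Step 1: how the criteria combine.** The sources are alternatives, and within the AE form the four items form a comma list closed by 'or'. In symbols:

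death = (term contains 'death') OR (outcome fatal) OR (result-in-death = yes) OR (death date present) OR (death on a Subject Status form)

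Nothing in SAP 6.5.1.1, 6.5 or 7.3 requires a fatal outcome alongside the term match, excludes the death of another person, or provides for review before tabulation.

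**Step 2: apply it to hypothetical records.** The comparison rule drops the first condition and keeps the other four.

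| Hypothetical record | Rule as written | Fatality field required |
|---|---|---|
| Alive; verbatim *grief after death of mother*; all fatality fields negative | counted | not counted |
| Alive; verbatim *bereavement*; 'death' not in the preferred term | not counted | not counted |
| Died; outcome fatal | counted | counted |
| Died; term *sudden death*; every other field blank | counted | not counted |

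Row 1 is the error. Row 2 shows its limit: the word itself must be present. Row 4 shows that simply deleting the criterion could lose a real death.

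**Step 3: follow the date.** Under SAP 7.3, last contact is the earliest complete death date on the AE form if there is one, and otherwise the latest of a long list of routine dates (diary, visits, laboratory, medications and others). The subject in row 1 has no AE death date. The last routine contact therefore becomes the death date.

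**Step 4: follow the period.** Under SAP 7.4, follow-up safety starts once more than 7 days have passed since the last dose of study drug. Protocol 4.3.5 places the 2-week follow-up visit 14 days after the end-of-treatment visit, with a window of 2 days either way, so no earlier than 14 − 2 = 12 days after it. If the end-of-treatment visit is on or after the last dose, then 12 > 7. At the final lock, a row 1 subject who attends that visit would have the false death placed in follow-up, whenever the event began. The same event would appear in the AE tables under the period of its own start date.

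**Step 5: how far it spreads.** Last contact is cut short only by a complete death date on the AE form. A term match does not do this, so time on study and follow-up are unchanged. Exposure runs on dosing dates and is also unchanged. The effect is confined to the deaths table and listing.

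**The case against.** The strongest reply is that over-capture is the safer error for deaths. Missing a real death is worse than listing a doubtful one, and row 4 shows that the term match can catch a death that every other field missed. The paired listing shows the sources, verbatim term, outcome and result-in-death answer, so a false entry would stand out as non-fatal with the AE term as its only support. With few entries, someone would be likely to notice. This stands as an argument against deleting the criterion outright. It does not rescue the table, because visibility in a listing does not change the count and no correction step is written.

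A second reply is that the BHV3000 Core SAP may cover the matter. SAP 6.5.1 says "Refer to the BHV3000 Core SAP for AE start date imputation, AE counting rules", and that document is not among those supplied. However, SAP 6.5.1.1 does not refer to it for identifying deaths. This remains a caution only.

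A reader might also infer more than the text supports:
- **That the reported deaths include false ones, or that their number can be estimated.** No such record is shown, and neither document gives a rate of non-fatal events with this word or an expected number of true deaths. Any estimate would rest on invented inputs.
- **That any bereavement-type event is caught.** Only terms that contain the word are.
- **That the death date is invented.** It is a real recorded contact date, wrongly labelled.

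**Conclusion.** The rule as written is wrong: followed exactly, it can count a living subject as a death by treatment group and safety period. Each term-only match in a living subject adds one to the table. The total effect cannot be sized from the documents and may be zero. This is a defect in the rule and not a demonstrated miscount. Efficacy, the AE tables, exposure and liver analyses are untouched.

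The conclusion rests on two assumptions: that the list is read with its plain 'or', and that the Core SAP adds no requirement to confirm or review deaths. It is worth correcting because the output matters and the change is small.

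**What to change.** Reword SAP 6.5.1.1 so that a subject counts as a death when at least one of these holds:
- the AE outcome is fatal;
- the result-in-death question is answered yes;
- a death date is present;
- death is the reason given on a Subject Status form.

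Keep the term match only as a flag. A record supported by the term alone goes to documented review before tabulation, and to a site query if the database is still open. It is counted only if the subject is confirmed to have died. Derive the death date in SAP 7.3 only for subjects who meet the revised rule.

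A pre-lock query alone would not be enough. The SAP revision history states that version 10.0 was made after the final database lock, so under the current plan the review step has to do the work. For outputs already produced, check in the deaths listing whether any tabulated death has the AE term as its only support, and correct the table if so.

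The cost is a short wording change, a small programming edit and a brief review of any flagged records.

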#### 6.5.1.2 AE Overviews

An AE overview without SOC and PT will present the number and percentage of subjects with any of the following AEs: any AE; mild AE; moderate AE; severe AE; AE related to study drug; SAE; SAE related to study drug; AE leading to study drug discontinuation; hepatic-related AE; severe hepatic-related AE; hepatic-related SAE; hepatic-related AE leading to study drug discontinuation; potential drug abuse AE; CV AE; and suicidality AE.

An AE overview will be produced by treatment group and overall for each the following safety analysis periods and populations:

- Pre-treatment for enrolled subjects (overall, not by treatment group)
- Pre-treatment for treated subjects
- Pre-rimegepant for DB or OL rimegepant treated subjects
- On-DBT for treated subjects (excluding overall)
- On-DBT for treated subjects limited to on-DBT TEAEs (excluding overall)
- On-DB or OL rimegepant for DB or OL rimegepant treated subjects
- On-DB or OL rimegepant for DB or OL rimegepant treated subjects limited to on-DB or OL rimegepant TEAEs
- Post-DBT pre-OL rimegepant for interim subjects
- Follow-up for follow-up subjects.

In addition, an AE overview will be produced by subgroup level and overall for all safety subgroups of interest described in Sections 6.1.3.3 and 6.1.3.4 for each the following safety analysis periods and populations:

- On-DB or OL rimegepant for DB or OL rimegepant treated subjects
  - On-DB or OL rimegepant for DB or OL rimegepant treated subjects limited to on-DB or OL rimegepant TEAEs
  - On-OL rimegepant for OL rimegepant treated subjects
-

- On-OL rimegepant for OL rimegepant treated subjects limited to on-OL rimegepant TEAEs.

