2.2 Secondary

- To compare the efficacy of rimegepant to placebo on the proportion of subjects that have at least a 50% reduction from baseline in the mean number of moderate to severe migraine days per month in the last 4 weeks of the double-blind treatment phase.
 - To compare the efficacy of rimegepant to placebo on the reduction from baseline in the mean number of migraine days per month over the entire course of the double-blind treatment phase.
 - To compare the frequency of use of rescue medications between the rimegepant and placebo in the last 4 weeks of the double-blind treatment phase.
 - To compare the efficacy of rimegepant to placebo on the reduction from baseline in the mean number of migraine days per month in the first 4 weeks of the double-blind treatment phase.
 - To evaluate the safety and tolerability of rimegepant.
 - To evaluate the frequency of ALT or AST > 3x ULN with concurrent elevations in bilirubin > 2x ULN in subjects treated with rimegepant.
 - To evaluate the frequency of hepatic-related adverse events and the frequency of hepatic-related treatment discontinuations in subjects treated with rimegepant.
 - To compare the change from baseline in the Migraine-Specific Quality-of-Life Questionnaire v 2.1 (MSQ) role function - restrictive domain score at Week 12 of the double-blind treatment phase between rimegepant and placebo.
 - To compare the change from baseline in the Migraine Disability Assessment (MIDAS) total score at Week 12 of the double-blind treatment phase between rimegepant and placebo.
-

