3.2 Secondary

- Achievement of at least a 50% reduction from baseline in the mean number of moderate to severe migraine days per month in the last 4 weeks of the double-blind treatment phase.
- Change from baseline in the mean number of migraine days per month over the entire double-blind treatment phase (Weeks 1 to 12).
- The mean number of rescue medication days per month in the last 4 weeks of the double-blind treatment phase. Rescue medications allowed in the 2 phases of this study are specified in Protocol Section 5.5.
- Change from baseline in the mean number of migraine days per month in the first 4 weeks (Weeks 1 through 4) of the double-blind treatment phase.
- The frequency of unique subjects with adverse events, serious adverse events, adverse events leading to discontinuation and clinically significant laboratory test abnormalities, from case report forms and clinical laboratory evaluations.
- The frequency of unique subjects with of AST or ALT elevations $> 3x$ ULN, concurrently with bilirubin elevations $> 2x$ ULN.
- The frequency of unique subjects with hepatic-related adverse events and hepatic-related adverse events leading to treatment discontinuation from case report forms.
- The mean change from baseline in the MSQ role function - restrictive domain score at Week 12 of the double-blind treatment phase.
- The mean change from baseline in the MIDAS total score at Week 12 of the double-blind treatment phase.

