9.5 Secondary Endpoint(s)

The number of subjects that experience at least a 50% reduction in the mean number of moderate or severe migraine days per month in the last 4 weeks of the double-blind treatment phase will be analyzed using a stratified Cochran-Mantel-Haenszel (CMH) test after the missing data are imputed as non-response.

The change from baseline in the mean number of migraine days per month over the entire double-blind treatment phase (Weeks 1 to 12) will be assessed with the same statistical model used to analyze the primary endpoint.

The use of rescue medications (mean number of days per month) in the last 4 weeks of the double-blind treatment phase will be assessed using a generalized linear mixed effects model that is similar in structure to that used for the primary analysis. Rescue medications are defined in Section 5.5.

The change from baseline in the mean number of migraine days per month in the first 4 weeks (Weeks 1 to 4) of the double-blind treatment phase will be assessed with the same statistical model used for to analyze the primary endpoint.

The investigators will determine the severity of adverse events (AEs) and the relationship of AEs to study therapy. The investigators' terms will be coded and grouped by system organ class using the latest version of the Medical Dictionary for Regulatory Activities (MedDRA) available to the analyst. AEs will be presented by system organ class and preferred term. If a subject had an adverse event with different severities over time, then only the worst severity will be reported. Tabulations will be made for the frequency of unique subjects with adverse events (by severity, by relationship to study drug, and overall), serious adverse events, adverse events leading to treatment discontinuation, hepatic-related adverse events (by severity, by relationship to study drug, and overall), and hepatic-related adverse events leading to treatment discontinuation from case report forms.

The frequency of unique subjects with clinically significant laboratory test abnormalities will be tabulated based on Grade 3 - 4 clinical laboratory evaluations graded using the latest version of Common Terminology Criteria for Adverse Events (CTCAE).

Other safety analyses will be described in the statistical analysis plan.

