Endpoint	Number and percentage of subjects with hepatic-related AEs and hepatic-related AEs leading to study drug discontinuation on treatment in the DBT and OLE phases
Pop. Summary	Frequency by treatment group and overall

Objective	MSQoL restrictive role function domain score change from baseline at Week 12 – Efficacy
Endpoint	Change from baseline in the MSQoL restrictive role function domain score at Week 12 in the DBT phase
Pop. Summary	Change from baseline by treatment group using descriptive statistics and model, and difference between treatment groups from model
Objective	MIDAS total score change from baseline at Week 12 – Efficacy
Endpoint	Change from baseline in the MIDAS total score at Week 12 in the DBT phase
Pop. Summary	Change from baseline by treatment group using descriptive statistics and model, and difference between treatment groups from model

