#### 6.5.1.4 *On-Treatment AEs*

##### **DBT Phase**

On-DBT AEs will be summarized by SOC and PT for treated subjects by treatment group for the following endpoints:

- AEs by severity
  - TEAEs by severity
  - TEAEs occurring with  $\geq 2\%$  frequency on rimegepant and greater than placebo after rounding. Percentages will be displayed rounded to integers, and AEs will be displayed in alphabetical order by SOC and PT.
  - AEs related to study drug by severity
  - AEs related to study drug occurring with  $\geq 2\%$  frequency in any treatment group
  - SAEs
  - AEs leading to study drug discontinuation
  - Hepatic-related AEs
  - Hepatic-related AEs leading to study drug discontinuation
  - Additional AEs of special interest: potential drug abuse, CV, and suicidality. Potential drug abuse AEs will be displayed in alphabetical order by severity and PT without SOC
  - Exposure-adjusted multiple occurrences of unique AEs (see Section 7.6.1)
  - Exposure-adjusted multiple occurrences of unique SAEs (see Section 7.6.1)
-

- Exposure-adjusted multiple occurrences of unique SAEs related to study drug (see Section 7.6.1)
- Exposure-adjusted multiple occurrences of unique non-SAEs occurring with  $\geq 5\%$  frequency in any treatment group (see Section 7.6.1).

AEs by severity will also be summarized analogously by subgroup level and overall for all safety subgroups of interest described in Section 6.1.3.2 for each treatment group.

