## 8 CHANGES TO PLANNED ANALYSES IN THE PROTOCOL

There are no changes to planned analyses in the protocol at this time.

---

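### The SAP's listed outputs omit the unique-subject count of drug-related hepatic AEs and the mild and moderate hepatic rows that Protocol 9.5 specifies, and SAP Section 8 does not declare the omission

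*SAP*

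**What the plan says.** Protocol 9.5 describes how safety endpoints will be tabulated by unique subject. It names the hepatic group separately from AEs in general and gives it its own splits: "hepatic-related adverse events (by severity, by relationship to study drug, and overall". It adds a count of hepatic events leading to discontinuation.

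The objective and endpoint are narrower. The objective in Protocol 2.2 is "To evaluate the frequency of hepatic-related adverse events and the frequency of hepatic-related treatment discontinuations in subjects treated with rimegepant". The endpoint in Protocol 3.2 counts unique subjects with "hepatic-related adverse events and hepatic-related adverse events leading to treatment discontinuation from case report forms". The SAP estimand follows the endpoint: "Number and percentage of subjects with hepatic-related AEs and hepatic-related AEs leading to study drug discontinuation on treatment in the DBT and OLE phases".

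SAP 6.5.1.2 gives the overview rows. For AEs in general these include "any AE; mild AE; moderate AE; severe AE; AE related to study drug; SAE; SAE related to study drug". For the hepatic group they are "hepatic-related AE; severe hepatic-related AE; hepatic-related SAE; hepatic-related AE leading to study drug discontinuation". SAP 6.5.1.4, under DBT Phase, lists tables by SOC and PT. The hepatic bullets there are a plain table of hepatic-related AEs and "Hepatic-related AEs leading to study drug discontinuation". The DB or OL Rimegepant Phase takes over the same list of endpoints.

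SAP Section 8 states: "There are no changes to planned analyses in the protocol at this time".

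**The concern.** The SAP states a split where it wants one. In 6.5.1.4, general AEs, TEAEs and drug-related AEs are each listed by severity, and even potential drug abuse events are displayed by severity. The hepatic bullets carry no such wording, although the protocol asked for both splits on that group.

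Protocol 1.3.1 names possible change in liver function tests as the main identified adverse event of interest, and Protocol 10.2 provides for no data monitoring committee. How many subjects in each arm had a hepatic event judged drug-related is a plain question that the protocol undertook to answer. As listed, the SAP's outputs do not answer it, and Section 8 gives the reader no sign that the plan was reduced.

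**Working it through.** The plan gives no figure to reproduce, so the check is a line-by-line comparison for the hepatic grouping. Severity grades are those defined in Protocol 8.1.1 (mild, moderate, severe).

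| Unique subjects with a hepatic-related AE | Protocol 9.5 | SAP 6.5.1.2 overview | SAP 6.5.1.4 tables |
|---|---|---|---|
| Any (overall) | yes | yes | yes |
| Mild | yes | no | no split stated |
| Moderate | yes | no | no split stated |
| Severe | yes | yes | no split stated |
| Related to study drug | yes | no | no split stated |
| Leading to discontinuation | yes | yes | yes |
| Serious | not specified for this group | yes | no |

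The overview has eight rows for AEs in general (any, mild, moderate, severe, related, serious, serious and related, leading to discontinuation) and four for the hepatic group. The four with no hepatic counterpart (8 - 4 = 4) are mild, moderate, related, and serious and related. Protocol 9.5 asks for the first three of these.

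The next question is whether the missing count can be recovered from other listed outputs.

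1. The 6.5.1.4 table of drug-related AEs by severity is by SOC and PT, by treatment group, with no frequency cut-off. Each drug-related hepatic preferred term therefore has a row. Rows cannot be added to give subjects. One subject with both ALT increased and AST increased contributes 1 + 1 = 2 to the sum of rows but is 1 subject. If the hepatic rows in an arm have counts n1, n2, ..., the number of subjects lies anywhere from the largest n to the sum of the n's. A SOC total does not settle it, because a SOC need not coincide with the hepatic grouping.
2. The tables of AEs and TEAEs by severity show hepatic terms at each grade, with the same limit for mild and moderate totals.
3. SAP 6.5.1 promises a by-subject listing of hepatic-related AEs. If it shows relationship, a reader could count by hand, but a listing is not a tabulation by arm, and its contents are set in the BHV3000 Core SAP.

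The gap recurs wherever the same lists are used: the overview for each safety period, the on-DBT tables, and the DB or OL rimegepant tables, including their subgroup version.

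**The case against.** The case against is strong on consequence. A reader might infer that drug-related hepatic events are never counted. The documents do not support that: each such term is counted by arm and severity in the general related-AE table, in both phases. A reader might also infer that a secondary objective goes unmet. It does not: the objective, the endpoint and the SAP estimand ask for the frequency of hepatic events and of hepatic discontinuations, without relationship or severity, and the SAP tabulates both. Nor is the placebo comparison of hepatic events lost. It is kept for any, severe, serious and treatment-ending events, and in a randomised phase the difference between arms does not depend on investigator attribution. SAP 6.5.2.2 adds LFT elevations, exposure-adjusted rates, time to first elevation, shifts, eDISH plots and by-subject plots.

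There is also a limit on what can be checked. SAP 6.5.1 sends AE counting rules, the definition of related AEs and listing contents to the Core SAP, and 7.1.1 puts table templates in the mock TLF documents. Neither was available, and a hepatic table split by severity or relationship in one of them cannot be ruled out.

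All of this stands, and it sets the size of the point. It does not remove the mismatch. The choice of AE tables is made in 6.5.1.2 and 6.5.1.4 of this SAP, nothing there promises the split, and Section 8 says that nothing changed.

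**Conclusion.** The point holds as a minor departure in descriptive safety reporting. Of the three hepatic breakdowns in Protocol 9.5, the overall count is kept, severity is cut to one grade of three, and relationship has no unique-subject count; the change is not declared. Protocol 9.5 attaches no test to these tabulations, so there is no effect on type I error, power or any efficacy conclusion. The conclusion assumes that the Core SAP and the mock tables add no split hepatic output. If they do, only a cross-reference is missing. It is still worth correcting, because the count concerns the main identified safety interest, was specified in advance, and cannot be built from preferred-term rows.

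**What to change.** In SAP 6.5.1.4, DBT Phase, change the hepatic bullet to *Hepatic-related AEs by severity* and add *Hepatic-related AEs related to study drug by severity*. Give each table a first row for subjects with any such event, so that it yields the unique-subject total. Both carry over to the DB or OL Rimegepant Phase through the existing reference. In 6.5.1.2 add a row for *hepatic-related AE related to study drug*. If the reduction was intended, state it in Section 8 instead.

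The cost is one or two extra tables per phase and one overview row. No new data are needed, since Protocol 9.5 already has investigators assess severity and relationship for AEs. The revision history says that version 10.0 was modified after the final database lock, for the Addendum Report, to correct errors and make analyses consistent. The tables would therefore be issued as a supplementary output and labelled as such.
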